10.3.3.3. Tertiary/Exploratory Analyses

- Proportion of patients achieving IGA of 0 or 1 with a ≥ 2 -point improvement at 2, 3, 4, and 5 years during long-term extension
- Proportion of patients achieving EASI75 at 2, 3, 4, and 5 years during long-term extension
- Proportion of patients achieving SCORAD75 at 2, 3, 4, and 5 years during long-term extension
- Frequency of patient-reported “no itch” (Itch NRS score = 0) days from daily diaries from Week 12 to Week 16
- Time to achieve a 4-point improvement in Itch NRS
- Frequency of patient-reported “no pain” (Skin Pain NRS score = 0) days from daily diaries from Week 12 to Week 16
- Mean change from baseline in the score of Item 1 of the ADSS at 1 week and 16 weeks
- Mean change from baseline in the score of Item 3 of the ADSS at 1 week and 16 weeks
- Changes from baseline in IgE levels during the study
- Changes from baseline in eosinophil levels during the study
- Characterization of baricitinib pharmacokinetics in the AD population and exploration of relationships between baricitinib exposure and study endpoints
- Assessment of efficacy outcomes in patients who choose to take a voluntary drug interruption (drug holiday) during Study Period 4
- Number of patients able to maintain control of AD signs and symptoms without use of TCS

Details of the tertiary/exploratory analyses will be further described in the SAP.

10.3.4. Safety Analyses

All safety data will be descriptively summarized by treatment group and analyzed using the safety population.

Treatment-emergent adverse events (TEAEs) are defined as AEs that first occurred or worsened in severity after the first dose of study treatment. The number and percentage of patients who experienced at least 1 TEAE will be summarized using MedDRA (Medical Dictionary for Regulatory Activities) for each Preferred Term within System Organ Class by treatment group. Serious adverse events and AEs that led to permanent discontinuation from the IP will also be summarized by treatment group. Special safety topics will be summarized and analyzed including the proportion and rate of patients developing skin infections requiring antibiotic treatment. Fisher’s exact test will be used to perform comparisons between each baricitinib dose and the placebo group, where applicable.

Clinical laboratory results will be descriptively summarized by treatment group. Individual results that are outside of normal reference ranges will be flagged in data listings. Quantitative clinical laboratory variables obtained at baseline and postbaseline visits will be summarized along with change from baseline by treatment group. Change from baseline to endpoint will be analyzed using ANCOVA with treatment and baseline value in the model. Categorical variables, such as treatment-emergent laboratory abnormalities, will be summarized by frequency and percentage. Shift tables will be presented for selected laboratory measures.

Observed values and changes from baseline for vital signs and physical characteristics will be descriptively summarized by treatment group and time point. Change from baseline to postbaseline in vital signs, height, and body weight will be analyzed using ANCOVA with treatment and baseline value in the model. Treatment-emergent abnormalities in vital signs (pulse and blood pressure) and weight will be evaluated based on pediatric standards.

A summary of temporary interruptions of study drug will be provided, showing the number of patients experiencing at least one temporary interruption and the number of temporary interruptions. Duration of each temporary interruption and the cumulative duration of interruptions using descriptive statistics will be provided.

Analyses of Growth (height, weight, and body mass index [BMI]):

Observed height velocity by sex and age group will be calculated at baseline and approximately every 3 months thereafter throughout the study:

- $(\text{Current Height [cm]} - \text{Previous Height [cm]}) / \text{Interval (months) between Measurements} \times 12$

Age-specific z-scores for height velocity by sex and age group will be calculated for each patient with reference to standard height velocity tables (from age- and sex- matched peers) according to the following formula:

- $(\text{Observed Height Velocity [cm/y]} - \text{Mean Height Velocity for Age and Sex [cm/y]}) / (\text{standard deviation of reference population})$

Similar analyses for weight and BMI velocity and z-scores will be conducted.

Data collected after initiation of rescue therapy will be summarized or listed where applicable.

More details of the safety analysis for this study will be provided in the SAP.

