
 To assess efficacy of baricitinib during longer-term treatment. 	
 Proportion of patients achieving IGA of 0 or 1 with a ≥ 2-point improvement at 1 year Proportion of patients achieving EASI75 at 1 year Proportion of patients achieving SCORAD75 at 1 year

 To assess growth and bone safety of baricitinib during longer-term treatment. 	
 Mean changes in growth (height and weight), growth velocity, and bone age over the course of treatment during the long-term extension treatment period
Tertiary/Exploratory Objectives	

 Frequency of patient-reported “no itch” (Itch NRS score = 0) days from daily diaries from Week 12 to Week 16 Frequency of patient-reported “no pain” (Skin Pain NRS score = 0) days from daily diaries from Week 12 to Week 16 Time to achieve a 4-point improvement in Itch NRS Mean change from baseline in the score of Item 1 of the ADSS at 1 week and 16 weeks Mean change from baseline in the score of Item 3 of the ADSS at 1 week and 16 weeks To evaluate changes from baseline in IgE levels during the study To evaluate changes from baseline in eosinophil levels during the study To characterize baricitinib pharmacokinetics in the AD population and explore relationships between baricitinib exposure and study endpoints Assessment of efficacy outcomes in patients who choose to take a voluntary drug interruption (drug holiday) during Study Period 4 Number of patients able to maintain control of AD signs and symptoms without use of TCS Proportion of patients achieving IGA of 0 or 1 with a ≥ 2-point improvement at 2, 3, 4, and 5 years during long-term extension Proportion of patients achieving EASI75 at 2, 3, 4, and 5 years during long-term extension Proportion of patients achieving SCORAD75 at 2, 3, 4, and 5 years during long-term extension 	

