5.1.1. Period 1: Screening

The duration of the Screening period is between 8 and 35 days prior to Visit 2 (Week 0). At Visit 1, the patient or parent/legal guardian will sign the informed consent form (ICF) prior to any study assessments, examinations, or procedures being performed. All screening procedures will be performed according to the Schedule of Activities (Section 2). Patients who receive a purified protein derivative (PPD) skin test at Visit 1 will need to return within 48 to 72 hours later to have the skin test read.

Patients Participating in Study Period 2 (PK Lead-in)

Patients who will participate in the open-label PK lead-in (Study Period 2) will be required to wash out of prior AD treatments as described in Section 6.1 (Study Population) and Section 7.7.

Patients Participating in Study Period 3 (Double-blind treatment)

Prior to randomization (Study Period 3), systemic treatments for AD will be washed out for 4 weeks. Certain topical treatments (not including emollients) will be discontinued prior to Visit 2 as described in Section 6.1 (Inclusion Criteria [6 c]) and Section 7.7. Sponsor-provided low- and medium-potency TCS will be given to patients at Visit 1, and patients will discontinue use of other TCS medications and begin use of the Sponsor-provided TCS medications as prescribed by the investigator (as clinically indicated). During the screening period, TCNIs (e.g., tacrolimus and pimecrolimus) or topical PDE-4 inhibitor (i.e., crisaborole, where approved) are permitted in place of TCS as on areas where application of TCS is considered inappropriate by the investigator; use should be limited to problem areas (e.g., face, neck, skin folds, genital areas, etc.).

All Patients

Patients will be required to use emollients daily during the 14 days preceding Visit 2 and throughout the study. If patients have been using emollients daily at the time of screening, then those cumulative days can be utilized to meet inclusion criterion [7]. Patients will receive a daily reminder via the daily diary to apply emollient. Additionally, collection of data through daily diaries will be required throughout the Screening period. The baseline for the daily patient-reported outcome (PRO) will be the average score of the 7 days prior to Visit 2; thus the minimum screening window was set at 8 days.

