5.1.4. Period 4: Long-term Extension Treatment Period

PK Lead-in Patients:

Patients participating in the PK lead-in period (Study Period 2) may proceed to the Long-term Extension period (Visit 9) 2 weeks after completing Visit 4 and continue to receive open-label baricitinib at the same dose they received in the PK lead-in. Patients may continue in the long-term extension for up to an additional 5 years (Figure JAIP.3).

Non-PK Lead-in Patients:

Patients who participate in the Double-blind Treatment period (Study Period 3) and complete through Week 16 (Visit 8) will be eligible to continue in the Long-term Extension period for up to 5 additional years of treatment (Figure JAIP.3). At Visit 8 (primary endpoint and end of the double-blind period), patients will be transitioned into the long-term extension treatment period as follows:

- Patients randomized to Double-blind Treatment who have achieved a response of IGA 0, 1, or 2 at Visit 8 (Week 16) without requiring rescue with topical treatments or systemic treatments during Study Period 3 will continue on the Double-blind Treatment to which they were randomized at Visit 2 (Week 0).

- Patients randomized to Double-blind Treatment who have not achieved a response (i.e., IGA of ≥ 3) or who have required rescue with topical treatments (i.e., high-/ultra-high-potency TCS) or systemic treatments during Study Period 3 will be transitioned to open-label baricitinib at the high dose for their age group.

All Patients:

During Study Period 4, patients are allowed to use TCS (all potencies), TCNI, and/or a PDE-4 inhibitor (e.g., crisaborole) as background treatments with IP if they experience worsening or lack of control of their AD.

During the first year of the extension treatment, use of background TCS, TCNI, and PDE-4 inhibitors is allowed as described in Section 7.7.2. During Study Period 4, for patients on double-blind treatment whose IGA worsens to 3 or 4 and who are unable to recapture an IGA response of 0, 1, or 2, despite the use of emollients and TCS, the patient may be transitioned at the discretion of the investigator to open-label baricitinib at the high dose for their age group.

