9.4.9.3. Growth Monitoring

Height and weight, left hand x-rays, knee x-rays, hormone levels, and occipital frontal circumference will be collected as described below and according to the Schedule of Activities (Section 2) to allow for the identification of potential effects on growth and development:

- Height measurements will be made using a stadiometer. Height measurements must be recorded to 1 decimal place without rounding.
- Weight measurements must be recorded to 1 decimal place without rounding.
- Instruments used for measuring height and weight should be appropriately and regularly calibrated.
- All measurements of height and weight should be made without shoes and after the removal of any heavy personal items (that is, large jewelry, wallets, coats, etc.).
- Height and weight changes in pediatric patients (both at an individual and group level) will be reviewed by the DMC external to Lilly.
- Left hand x-rays will be collected to assess effects on bone age.
 - Ongoing patients will have hand x-rays completed approximately every 6 months per the Schedule of Activities (Section 2) after approval of this protocol amendment and completion of the consent form. A central vendor will be used for reading of the x-ray images.
- Knee x-rays will be collected to monitor bone growth.

- An x-ray of the knee (anteroposterior) will be collected approximately every 6 months as shown in the Schedule of Activities (Section 2). A central vendor will be used for reading of the x-ray images.
- Ongoing patients will have a knee x-ray at the next scheduled visit after approval of this protocol amendment and completion of the consent form. Subsequent knee x-rays will be collected per the Schedule of Activities (Section 2), unless the subsequent visit is within 3 months of the first knee x-ray, in which case the knee x-ray can be skipped at this timepoint to avoid unnecessary radiation exposure.
- If a local addendum is in place that specifies another mode of imaging (e.g., magnetic resonance imaging [MRI] instead of x-ray), the local addendum should be followed. Otherwise, the current protocol amendment should be followed with regard to knee x-rays.
- Any symptomatic areas of bones/joints will be assessed and investigated as appropriate by study investigators. Any diagnoses made based on symptomatic areas of bones/joints or imaging data will be reported as appropriate (e.g., recorded on eCRF).

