10.3. Statistical Analyses

10.3.1. General Statistical Considerations

Statistical analysis of this study will be the responsibility of Lilly or its designee. A detailed SAP describing the statistical methodologies will be developed by Lilly or its designee.

Any change to the data analysis methods described in the protocol will require an amendment ONLY if it changes a principal feature of the protocol. Any other change to the data analysis methods described in the protocol, and the justification for making the change, will be described in the clinical study report (CSR). Additional exploratory analyses of the data will be conducted as deemed appropriate.

All tests of treatment effects will be conducted at a 2-sided alpha level of 0.05, unless otherwise stated (e.g., refer to Section 10.3.7.3). Treatment comparisons of discrete efficacy variables between baricitinib and placebo will be made using a logistic regression analysis with region, disease severity, age, treatment group, and treatment group-by-age interaction in the model. The percentages, difference in percentages, and 95% confidence interval (CI) of the difference in percentages will be reported. Treatment-by-age interaction will be added to the logistic regression model of the primary and key secondary variables as a sensitivity analysis. If this interaction is significant at a 2-sided 0.1 level, further inspection will be used to assess whether the interaction is quantitative (i.e., the treatment effect is consistent in direction but not size of effect) or qualitative (the treatment is beneficial for some but not all age groups). The p-value from the Fisher exact test will also be produced.

When evaluating continuous measures over time, a restricted maximum likelihood-based mixed-effects model of repeated measures (MMRM) will be used. The model will include treatment, age cohort, baseline severity, visit, and treatment-by-visit interaction, and treatment-by-age cohort interaction as fixed categorical effects and baseline score and baseline score-by-visit interaction as fixed continuous effects. Region may be included in the model if

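### Baseline height and BMI velocity cannot be computed because no height is scheduled before Visit 2, and the height and weight ANCOVA forgoes precision by omitting age and sex

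*Protocol*

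**What the plan says.** Protocol Section 10.3.4, under the growth analyses, states: "Observed height velocity by sex and age group will be calculated at baseline and approximately every 3 months thereafter throughout the study". Velocity is the current minus the previous height, divided by the months between the two, times 12. Each patient's velocity z-score subtracts an age- and sex-specific mean and divides by the SD of a reference population. The reference tables are not named and their interval is not given. The section adds: "Similar analyses for weight and BMI velocity and z-scores will be conducted".

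Section 2 sets the heights. In Table JAIP.2 (randomised patients) the first is at Visit 2 (Week 0), then Week 16, Week 28 and every 12 weeks. In Table JAIP.1 (PK lead-in patients) the first is also at Visit 2, then Week 16 and every 12 weeks. Visit 1 has a weight but no height. Section 9.4.9.3 adds: "Height measurements must be recorded to 1 decimal place without rounding".

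On the model, Section 10.3.4 says: "Change from baseline to postbaseline in vital signs, height, and body weight will be analyzed using ANCOVA with treatment and baseline value in the model". The efficacy model for discrete outcomes in Section 10.3.1, by contrast, is a "logistic regression analysis with region, disease severity, age, treatment group" model with a treatment-by-age term. Randomisation (Section 7.2) is stratified by IGA and possibly region, not by age or sex.

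Growth is a secondary objective (Section 4, Table JAIP.3), with the endpoint "Mean changes in growth (height and weight), growth velocity, and bone age over the course of treatment during the long-term extension treatment period".

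**The concern.** Two statements in the growth plan do not fit the rest of the protocol.

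- **Baseline velocity.** A difference between two heights is requested at a visit where only the first height exists. The SAP cannot supply a value for data that are not scheduled; it can only drop the time point or redefine it.
- **Covariates.** Growth over 16 weeks depends strongly on age and sex in a population aged 2 to <18. The model adjusts for the baseline value alone, although both variables are collected and age is already in the efficacy model.

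A third matter is conditional. A short interval scaled up to a year also scales up measurement error. If such a velocity is divided by an annual reference SD, extreme individual z-scores will be commoner than the reference implies, in both directions.

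At stake are a clean definition of a secondary safety endpoint in children, the precision of the only randomised growth comparison, and the readability of individual z-scores.

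**Working it through.** The protocol gives no figure of its own to reproduce, so its formula is applied to its own schedule.

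**1. Is there a previous height at baseline?** Scheduled heights fall at Weeks 0, 16, 28, 40, 52 and so on. At Week 0 there is one height and no interval, so velocity is undefined. BMI needs height, so BMI velocity is undefined too. The first computable value is Weeks 0-16.

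**2. Annualising factor, 52/w for a gap of w weeks.** One recording step is 0.1 cm.

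- 12 weeks: 52/12 = 4.33, so one step is 0.1 x 4.33 = 0.43 cm/y.
- 16 weeks: 52/16 = 3.25, so one step is 0.33 cm/y.
- 52 weeks: factor 1, so one step is 0.10 cm/y.
- With the ±7-day windows at both ends, a 12-week gap is 70 to 98 days, and the factor runs from 365.25/70 = 5.2 to 365.25/98 = 3.7.

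**3. Dispersion of individual z-scores, if the reference is annual.** Assumptions, none from the protocol: single-height error SD s = 0.1 to 0.5 cm; annual reference SD R = 0.8 to 1.2 cm/y, already containing the error of two heights a year apart; no true within-year variation in growth; a descriptive cut-off of z < -2, where 2.3% is expected. Then

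SD(z) = sqrt(1 + 2 s² ((52/w)² - 1) / R²), and P(z < -2) = Phi(-2 / SD(z)).

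Low case s = 0.1, R = 1.2; middle s = 0.3, R = 1.0; high s = 0.5, R = 0.8. For the middle case at 12 weeks: sqrt(1 + 0.18 x 17.78) = 2.05, and Phi(-2/2.05) = 16.5%.

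| Gap (weeks) | SD(z), low to high | P(z < -2), low / middle / high |
|---|---|---|
| 12 | 1.12 to 3.86 | 3.7 / 16.5 / 30.2% |
| 16 | 1.06 to 2.91 | 3.0 / 11.3 / 24.6% |
| 24 | 1.03 to 1.97 | 2.6 / 6.1 / 15.5% |
| 28 | 1.02 to 1.71 | 2.5 / 4.8 / 12.1% |
| 48 | 1.00 to 1.07 | 2.3 / 2.4 / 3.0% |
| 52 | 1.00 | 2.3% in all cases |

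The upper tail is the same by symmetry. Measurement error has mean zero here, so group means are not shifted.

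**4. Precision lost by omitting age and sex in Period 3.** If they explain a share R2 of the variance left after the baseline value, adding them cuts the standard error by 1 - sqrt(1 - R2):

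- R2 = 0.1: 1 - sqrt(0.9) = 5.1%.
- R2 = 0.4: 1 - sqrt(0.6) = 22.5%.

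A simulation with 110 patients per arm and an invented growth curve gave standard errors of 0.110 cm without and 0.084 cm with age and sex (a cubic in age, separately by sex). That is just under a quarter, near the top of this range. The treatment estimate was unbiased either way.

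**The case against.** **Little is lost at baseline.** True. The endpoint concerns the extension and can be estimated from Week 16 on. A reader might infer that the growth-velocity endpoint cannot be estimated; the schedules do not support that. Sites may take an unscheduled height at screening, since exclusion criterion 18 uses height percentiles, but the protocol does not collect one for this purpose. Over the 8 to 35 days of screening it would be multiplied by 365.25/35 = 10.4 to 365.25/8 = 45.7.

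**Weight.** Weight is taken at Visits 1 and 2, so a reader might infer that the plan annualises that screening gap. The sentence extending the analyses to weight does not clearly ask for it, so this is not part of the point.

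**The z-score point belongs to the SAP.** Largely right. The reference and its interval may properly be set there, and the text does not say that the previous height must be the immediately preceding one. The protocol defines no z cut-off and attaches no action to one. The table's high case is extreme: error variance is 0.50 of a reference variance of 0.64. Only the factor of 4.33 and the 0.43 cm/y step come from the documents. A reader might infer that the velocity analysis will yield false growth signals; without the reference, that does not follow.

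**Age and sex are already used.** They are built into the velocity summaries and the matched z-scores, which softens the ANCOVA point but leaves that model's stated covariates unchanged. A reader might infer bias. In Period 3 randomisation rules that out, and only precision is lost. In the extension, treatment depends on response and rescue (Section 5.1.4). Adding age and sex would not remove that confounding, and the text does not say the ANCOVA is used to compare arms there.

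**Conclusion.** The baseline point stands on the protocol's own text: height velocity at baseline, and likewise BMI velocity, cannot be computed from the scheduled heights. The loss is confined to that one time point.

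The ANCOVA point also stands, as a precision matter in Period 3. Its size, 5-23% of the standard error, rests on the assumption that age and sex explain 10-40% of the residual variance.

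The over-dispersion of 12-week z-scores is secondary and conditional. It holds if the reference tables are annual and consecutive heights are used, and it affects individual values, not group means. Its direction is clear under those conditions; its size rests on assumed error and reference SDs.

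None of this invalidates the growth endpoint.

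**What to change.** - Delete the baseline time point for height and BMI velocity. Use the Visit 2 height-for-age z-score as the baseline and its change as an outcome, available at every height visit from Week 16.
- Add age and sex to the height and weight ANCOVA. The form of the age term can be set in the SAP; growth is not linear in age over 2 to <18 years.
- Keep the Weeks 0-16 velocity as the randomised comparison. It is the only scheduled velocity interval wholly inside placebo-controlled treatment.
- For individual velocity z-scores, name a reference matched to the interval, or add windows of about 6 to 12 months (Weeks 0-28, then 24-week windows; Weeks 0-52, then 48-week windows). Note that windows crossing Week 16 mix randomised and open-label exposure, because patients with IGA of 3 or more, or with rescue, move to the open-label high dose then, including patients from placebo.
- Describe growth comparisons in the extension as non-randomised.

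The cost is wording and a little extra programming, with no new data. Longer-window z-scores arrive later, at Week 28 or Week 52, so they should be added to the Weeks 0-16 velocity and not replace it.
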